510	instrument) for reporting quality indicators at all nine A2ALL centers (see Appendix
511	F), the investigators will:
512	 Assess overall patient satisfaction with pain management
513	• Assess satisfaction with aspects of pain management thought to affect overall
514	patient satisfaction
515	 Identify quality indicators that differ in overall donor satisfaction
516	
517	

517 **3.6.2** Hypothesis

518 Using these methods, we reason that individual centers may perform equally well using different 519 approaches to pain management and suggest that variations in the quality of a patient's experience

520 will be influenced by the structure and process of care.

521 4 Investigational Plan

5224.1Primary Aim 1: To collect data and biosamples prior to, during, and after LDLT among523all donors and recipients for use by other A2ALL protocols and future studies.

524 4.1.1 Study methods

525 In order to maximize the study population, there are several cohorts of subjects who will enter the 526 protocol, based on:

• Their previous enrollment in the original A2ALL Cohort Study.

- Whether their clinical care occurred/is occurring at one of the new consortium centers.
 When the project was renewed, three of the original A2ALL clinical centers' funding was not renewed, and three new centers were added to the consortium (University of Toronto, Lahey
- 531 Clinic and University of Pittsburgh Medical Center).
- When the transplant/donation occurred. In order to have a contiguous sample, those subjects from the original sites and new sites whose transplant/donation occurred during the period of time that began with the end of enrollment into the original Cohort study (Aug. 31, 2009) and ends with opening of enrollment in the current core protocol (February, 2011); this is referred to as the "Gap Era".
- 537 Subjects who enroll after their donation/transplant will join the protocol schedule of events at the
- 538 next scheduled visit time point in the study, with interim data collected by chart review. Those who 539 have already reached study endpoints (death or graft failure) will have follow-up data collected
- 539 have already reached study endpoints (death of gran failure) will have 1 540 through the endpoint under waiver of consent.
 - 541 Enrollment for LDLT recipients and donors who were not in the A2ALL-1 Cohort Study or from the 542 gap era will occur prior to living donation.

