626	0	Plasma and peripheral blood cells – collected pre-operatively, and post-operatively at
627		Month 1, Month 3, Month 12, and Month 24 postoperatively, for storage in the
628		NIDDK repository
629	0	Whole blood for extraction of RNA – collected pre-operatively, and post-operatively
630		at Month 1, Month 3, Month 12, and Month 24 postoperatively, for storage in the
631		NIDDK repository
632	0	Liver tissue collected intraoperatively while graft is on the back table, and 1 hour
633		after arterial and portal venous reperfusion prior to closure for storage in the NIDDK
634		repository and for genomic analysis of regeneration
635 • E)onor	'S
636	0	LFTs - baseline, postoperatively at Week 1, Month 1, Month 3, Month 12 and
637		annually thereafter
638	0	CBC - baseline, postoperatively at Week 1, Month 1, Month 3, Month 12 and
639		annually thereafter
640	0	BUN and serum creatinine - baseline, postoperatively at Week 1 and Month 1
641	0	Coagulation (PT/INR) - baseline, postoperatively at Week 1, Month 1, Month 3,
642		Month 12 and annually thereafter
643	0	Demographics
644	0	Relationship to recipient
645	0	Intraoperative data (lobe donated, estimated blood loss, donated lobe weight, length
646		of operation, etc.).
647	0	Liver tissue collected intraoperatively just prior to resection, closest to the line of
648		resection and at one hour post-resection, or prior to closure, for storage in the NIDDK
649		repository and for genomic analysis of regeneration
650	0	Medical history
651	0	Post-operative morbidity
652	~	Imaging studies of the liver and spleen pre-operatively and at 3 months post-donation
	0	industry und a provide and speed pro-operatively and at 5 months post donation
653	0	Hospitalizations

- 654 o Whole blood collected for genetic analysis/DNA studies for extraction by the
 655 study's contracted DNA Core Lab (Fisher Bioservices), and storage in the NIDDK
 656 Biorepository (one-time collection)
- 657 o Serum collected preoperatively and postoperatively at Week 1, Month 1, Month 3,
 658 Month 12 for storage in the NIDDK repository
- 659
 Plasma and peripheral blood cells collected preoperatively, and at Month 1, Month
 3, and Month 12 postoperatively, for storage in the NIDDK repository
- 661
 662
 Whole blood for extraction of RNA collected preoperatively and postoperatively
 662
 Month 1, Month 3, and Month 12 for storage in the NIDDK repository.

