1228 4.6.1.3 Participant Selection – Retrospective Component

- 1229 The lead investigator at each site will select up to three health care providers involved in post liver
- 1230 donation pain management: a liver transplant surgeon, an anesthesiologist, and the nurse transplant 1231 coordinator.
- 1232 4.6.1.4 Participant Selection – Prospective Component
- 1233 Inclusion Criteria

1234

- Adult living liver donors
- 1235 **Exclusion** Criteria
- 1236 History of chronic pain •
- History of narcotic use (routine scheduled narcotic use for treatment of a pain disorder 1237 1238 diagnosed and treated by a physician)
- 1239 Medically unstable at 48 hours post-donation surgery •
- 1240 Language barrier •
- 1241 4.6.1.5 Data elements
- 1242 **Retrospective Component:**
- 1243 Responses to retrospective survey (see Appendix E)
- **Prospective Component** 1244
- 1245 Demographic information as described in Section 4.1.3 •
- 1246 Intraoperative, perioperative and post-operative complication and hospitalization information • as described in Section 4.1.3 1247
- 1248 Responses to screening questions regarding history of chronic pain and narcotic use •
- Responses to the APS-POQ-R survey (see Appendix F) 1249 •
- 1250 4.6.1.6 Sample size and power calculations
- 1251 Retrospective Component: The unit of analysis is the clinical center, with a sample size of 9. This
- analysis will describe clinical practice at the 9 A2ALL centers and will not attempt to make 1252
- 1253 inference to a larger population.
- 1254 Prospective Component: We anticipate that approximately 200 future donors will be enrolled in 1255 A2ALL-2. Although it is unlikely that more than 200 donors will be accrued, enrollment will
- 1256 remain open during A2ALL-2 to allow as much power as possible to assess center effects and
- variables predictive of satisfaction with pain management. Because many of the study measures will 1257
- 1258 be presented descriptively, we first give the confidence interval (CI) width for, e.g., the true mean
- 1259 satisfaction score (0-10 scale) assuming a standard deviation of 2.0. With n=200, we will have 93%
- probability that the width of this CI will be no greater than +/-0.30. For comparing the satisfaction 1260 1261 scores at two of the 9 centers, say each with n=30 donors, we will have 90% power to detect a
- 1262 difference in means of 1.7. Sample size calculations were made using the SAS Power procedure
- 1263 (SAS Institute, Inc., Cary, NC).

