1264 4.6.1.7 Statistical Analysis

- 1265 Retrospective Component:
- 1266 The methods and personnel that each center uses to manage postoperative pain in live liver donors
- 1267 and methods they have stopped using, will be presented using descriptive statistics. If possible,
- 1268 graphical methods will be used to display the changes over time.

1269 The medical specialty of care providers responsible for pain management and assessment will also

- be described for the 9 A2ALL centers. This summary will include both the type of specialists
 involved, and whether pain management involved an Acute Pain Team or not. Both the proportion
- 1271 of centers with Acute Pain Teams and the composition of these teams will be described. The
- 1273 continuity of pain management through phases of patient locations (e.g., ICU, surgical ward) will
- 1274 also be reported. Finally, the opinion of the medical care providers on the adequacy of pain control
- 1275 at their center will be described, and will also be compared to patient reports at that center (using
- 1276 data from prospective component of the study).
- 1277 Prospective Component:
- 1278 Satisfaction will be assessed using (a) the single question (P9), measuring overall satisfaction, and
- (b) the individual items of the pain questionnaire (P1-P8 and P10-12). These outcomes will be

1280 presented using descriptive statistics, including frequencies, means and standard deviations.

1281 Histograms and/or boxplots will be used to identify the forms of the distributions and to identify

- 1282 outliers. Aspects of care with low scores or a large standard deviation will be identified as practices
- 1283 that require overall improvement. Boxplots and analysis of variance will also be used to display and
- 1284 compare quality indicators from the APS-POQ-R measures by center.
- 1285 To identify aspects of care that account for differences in patient satisfaction, we will evaluate 1286 predictors of overall satisfaction (P9) using linear regression. Predictors of overall satisfaction to be
- 1287 tested will include the pain relief variables (P1-P7), participation in decisions about pain treatment
- 1288 (P8), helpfulness of information received (P10), non-medicine methods of treatment (P11, P12),
- 1289 demographic variables, and donor relationship.
- 1290 The complications outcomes (P6) will be analyzed using descriptive statistics as described above.

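### Aim 6 compares centres on pain-care indicators with no donor covariates, so centre differences could partly reflect donor mix, lobe donated in particular

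*Protocol*

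**What the plan says.** Section 3.6.2 suggests that "individual centers may perform equally well using different" approaches, and that differences in the quality of a patient's experience "will be influenced by the structure and process of care".

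For the prospective component, 4.6.1.7 states the centre comparison in one sentence: "Boxplots and analysis of variance will also be used to display and" "compare quality indicators from the APS-POQ-R measures by center". Centre is the only factor given.

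The next paragraph evaluates "predictors of overall satisfaction (P9) using linear regression. Predictors of overall satisfaction to be" tested then follow as a list: items P1 to P8 and P10 to P12, "demographic variables, and donor relationship". Centre and lobe donated are not on it.

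The donor data already exist. Aim 6 lists "Demographic information as described in Section 4.1.3" among its data elements (4.6.1.5). Section 4.1.3 collects each donor's relationship to the recipient and "Intraoperative data (lobe donated, estimated blood loss, donated lobe weight, length" of operation, among other items. The table at the start of Section 3 places A2ALL-2 donors in both Aim 1 and Aim 6, so these are the same people.

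Section 4.6.1.6 keeps enrolment open partly to gain power for centre effects, and gives a power statement for comparing two centres.

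**The concern.** Aim 6 is about how the organisation and delivery of pain care relate to the donor's experience. A comparison by centre bears on that only if donors at different centres are alike in other respects, or are made comparable in the analysis. Section 4.4.1 says that right lobe, left lobe or left lateral segment is used according to clinical parameters. Section 2.5.1 contrasts a left-lobe resection of about 40% of the liver with removal of more than half. If the mix of resections differs between centres, and extent of surgery affects pain or satisfaction, centres with identical care will show different means. The same mechanism can hide a real difference.

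The P9 regression does not close the gap. It covers one indicator, omits centre, and omits lobe. For every other indicator, no stated model relates a centre difference to donor characteristics. This matters because 2.7 says the data can be used to set quality-based goals for pain management, and 3.6.1 aims to find areas for improvement.

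**Working it through.** **The plan's own figures.** Inputs from 4.6.1.6: SD 2.0 on a 0-10 scale; n = 200 overall; two centres of 30; difference 1.7. Two-sided alpha of 0.05 is assumed, since none is stated for Aim 6.

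- Two-centre power: noncentrality = 1.7 / (2.0 × √(2/30)) = 1.7 / 0.516 = 3.29. The two-sample t test then has power 0.899, against the stated 90%.
- Precision: expected half-width = 1.972 × 2.0 / √200 = 0.279. The probability that it is at most 0.30 is 0.936, against the stated 93%.

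Both reproduce. The point concerns possible confounding, not an arithmetic error.

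**Size of a false centre difference.** The documents give neither the lobe mix by centre nor the effect of lobe on any indicator, so both are assumed and varied.

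- Nine centres (k = 9), n = 200/9, taken as 22 donors each; SD 2.0; care identical everywhere.
- Left-lobe share rises evenly across centres from 0 to R, with R = 0.2, 0.3 or 0.6.
- A smaller resection is worth b = 0.5, 1.0 or 1.5 points.

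Centre means differ only through b × share. For nine equally spaced shares the sum of squared deviations is 60 × (R/8)² = 0.9375 R². The noncentrality of the one-way F test is

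λ = n × b² × 0.9375 R² / SD² = 22 × 0.9375 × b²R² / 4 = 5.16 b²R².

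With 8 and 189 degrees of freedom the 5% critical value is 1.99. Rejection rates are:

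| Left-lobe share | b = 0.5 | b = 1.0 | b = 1.5 |
|---|---|---|---|
| 0-20% | 5.2% | 5.7% | 6.5% |
| 0-30% | 5.4% | 6.5% | 8.7% |
| 0-60% | 6.5% | 12.1% | 23.8% |

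For example, b = 1.5 and R = 0.6 give λ = 5.16 × 2.25 × 0.36 = 4.18 and a rejection rate of 23.8%. If the lobe effect adds to the within-centre variance instead of being part of the 2.0, this cell falls to 21.8% and the others change less.

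**With adjustment.** In simulations of the 0-20%, 0-30% and 0-60% settings, adding lobe to the model returned the rejection rate to 4.6-5.4%.

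**Scale of the bias.** The largest false difference between two centres is b × R: 1.5 × 0.3 = 0.45 points at a 30-point spread and 1.5 × 0.6 = 0.90 at 60. Both are below the 1.7 points for which 4.6.1.6 claims 90% power.

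**The case against.** The strongest reply is that the protocol never says the comparison is unadjusted. It is silent on covariates, and a statistical analysis plan, which is not at hand, might add them. That has some force. But 4.6.1.7 does fix a method and its factor, and it lists predictors for the neighbouring model. Elsewhere the protocol names adjustment where it intends it: Aim 5 adjusts for centre experience (4.5.3) and for covariates such as age and MELD score (4.5.5). Changing a stated method is more than supplying missing detail.

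Three stronger readings are tempting, and the documents do not support them.

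- A reader might infer that Aim 6 attributes centre variation to care. Section 3.6.2 is tentative: it says centres may do equally well and that experience is influenced by care, not determined by it. The analysis of variance is there to display and compare. No text says that a centre difference will be read as a care difference or used to rank centres.
- A reader might infer that age and sex are ignored in Aim 6. They would normally fall under the demographic variables in the P9 regression, so lobe donated is the example that stands for satisfaction.
- A reader might infer a badly inflated error rate. Spreading left-lobe share over 0-90% does push rejection to about half of studies at 1.5 points. But 2.5.1 says that nearly all A2ALL-1 transplants used the right lobe. It hopes for more left lobes but gives no share and no difference between centres.

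Two further points stand as limits. Section 2.7 reports that satisfaction depends heavily on interaction with care providers and that little pain did not guarantee it, so a large lobe effect on P9 is not assured. The exclusions for chronic pain and routine narcotic use (4.6.1.4) remove some case mix, though they do not touch lobe.

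**Conclusion.** The point holds in a limited form. The stated centre comparison names no donor covariate, and the one multivariable model contains neither centre nor lobe. Differences between centres could therefore partly reflect donor mix rather than the structure and process of care.

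The size cannot be known from the protocol. If left-lobe grafts stay a minority everywhere (shares up to 20% or 30%), the excess over 5% is negligible to small. It becomes material only if lobe mix differs widely between centres and the effect is a point or more. These figures assume a linear gradient of shares, equal centre sizes, and the satisfaction SD of 2.0; other indicators may behave differently. The case for change rests on its low cost and on the fit between analysis and hypothesis, not on a demonstrated large bias.

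**What to change.** In 4.6.1.7, compare centres by analysis of covariance with centre as the factor and donor age, sex, lobe donated and donor-recipient relationship as covariates. Lobe and relationship are recorded under 4.1.3; age and sex are taken to be among its demographics. Do not adjust for pain technique or other process variables, because these are what the hypothesis is about. Report adjusted centre means with confidence intervals beside the raw boxplots.

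The cost is a few of the roughly 189 residual degrees of freedom (198 donors less nine centre means) and one added table, with no new data. Lobe should be tabulated by centre as well: where a centre uses one type almost exclusively, its adjusted mean leans on the lobe effect estimated at other centres. If adjustment is not wanted, the section should say that the centre comparison is descriptive only.

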- 370 The following table shows the categories of patients that are relevant for each of the Aims (1 through 6) below (R=recipients; D=donors). 371
- 372

		Era of Transplant or Donation		
		A2ALL-1 Cohort (or	Gap	A2ALL-2
		analog at new centers)		
Continuing	LDLT	R: 1,2,5; D: 1,3	R: 1,2; D: 1	R: 1,2,4; D: 1,3,4,6
A2ALL -1	DDLT	R: 1,2,5;		
Centers				
New A2ALL	LDLT	R: 1,2,5; D: 1,3	R: 1; D: 1	R: 1,4; D: 1,3,4,6
Centers	DDLT	R: 5;		

373

374 3.1 Primary Aim 1: To collect data and biosamples prior to, during, and after LDLT among 375 all donors and recipients for use by other A2ALL protocols and future studies.

376 **3.1.1 Objectives**

- To facilitate and inform studies of samples and data collected, thus enhancing the value of
 this and future investigations.
- To continue contributing to the NIDDK genetics, biosample and data repositories so that
 current and future questions regarding liver disease, living donation and liver transplantation
 can be investigated by A2ALL and external researchers as new technologies and resources
 become available.
- To ensure that samples are stored under uniform conditions, and to simplify access by other
 scientists to samples. Similarly, study datasets will be maintained to facilitate new analyses
 after the study closes.

386 3.2 Primary Aim 2: To characterize the differences between LDLT and DDLT in terms of recipient post-transplant outcomes including patient and graft survival, surgical morbidity, and resource utilization.

389 **3.2.1** Objectives

392 393

394 395

- To continue to discern the long-term risks and benefits associated with choosing a living donor vs. deceased donor liver transplant with respect to the following metrics:
 - Patient and graft survival analysis starting from the time of transplantation
 - Comparison of the incidence of defined medical and surgical complications after transplant between LDLT and DDLT
 - Comparison of resource utilization (hospitalization) between LDLT and DDLT.

396 3.3 Primary Aim 3: To determine the prevalence, course, and predictors of poor HRQOL outcomes associated with living liver donation.

- Measures used to broadly assess HRQOL in A2ALL to date (e.g., SF-36) will be augmented with assessments of specific domains that reflect important difficulties that liver donors appear to face not only in the early years, but long after donation.
- 401 A cohort will be assembled consisting of (a) all A2ALL donors previously enrolled in A2ALL from

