4.2 Primary Aim 2: To characterize the differences between LDLT and DDLT in terms of recipient post-transplant outcomes including patient and graft survival, surgical morbidity, and resource utilization.

666 **4.2.1 Study methods**

- 667 In the A2ALL-1 Cohort Study, recipient candidates who were eligible to receive a living donor graft,
- but received a deceased donor graft (DDLT) were followed in the study. In order to characterize
- 669 differences between DDLT and LDLT post-transplant outcomes, DDLT recipients who participated
- 670 in the A2ALL Cohort Study will be approached for consent into the A2ALL-2 Core Protocol for
- 671 continued data and specimen collection.
- 672 A2ALL-1 Cohort Study LDLT and DDLT recipients will join the protocol at whatever post-
- transplant time point they have reached, with interim follow-up data collected by chart review.
- Those who have already reached study endpoints (death or graft failure) will have follow-up data
- 675 collected through the endpoint by waiver of consent.
- All A2ALL centers will consent and enroll willing eligible LDLT recipients from the "Gap Period"
- 677 who have not yet met study endpoints, with retrospective data obtained by electronic medical
- 678 records or chart review; for those who have met study endpoints, data will be collected under waiver
- 679 of consent. Prospective post-transplant data and biosamples will be collected from this population as
- 680 is described in Primary Aim 1 for LDLT recipients.

681 4.2.2 Participant Selection

- All potential subjects will be presented with information and approached for consent to have their
 biosamples, genetic material and deidentified data stored in the NIDDK repositories for future study.
 Please see Appendix D to view a table detailing subject eligibility by site type, graft type and study
 era.
- 686 4.2.2.1 Inclusion Criteria
- Age 18 or older at the time of consent
- Had a living donor identified and receipt of an LDLT was or is planned, and
- Received an LDLT graft, or donated in the Gap Period (all sites)
- Received a DDLT graft (continuing sites only)
- Participated in the A2ALL-1 Cohort Study (continuing sites only)
- 692 Informed consent obtained

693 **4.2.2.2 Exclusion criteria**

• Prospective subjects should not have undergone transplant/donation surgery prior to consent.

695 4.2.3 Data elements

696 See Section 4.1.3.

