We anticipate enrollment to average 10 recipients annually per site with a potential enrollment of 180 recipients over a 2-year period. This sample size estimate is based on the numbers of living liver donor transplants performed at A2ALL-2 sites during the past 3 years and the expectation that we would enroll subjects for a total of two years going forward (allowing for follow-up of the last subjects enrolled before the end of A2ALL-2 funding). It also assumes 20% to 30% of prospective recipients will refuse to enroll. Statistical analysis

- 1001 The chief aim of the analyses is to provide descriptive information about relation between hepatic
- 1002 hemodynamics and graft size and functional outcomes. Standard approaches to examine
- 1003 distributions (e.g., descriptive statistics, box plots, histograms). We will attempt to identify
- 1004 correlations using regression analysis. Categorical comparisons between graft types will be
- 1005 examined to detect the effect of left lobe grafting.

10064.5Primary Aim 5: To compare the long-term histological outcomes in recipients of LDLT1007and DDLT with recurrent HCV infection

1008 **4.5.1 Study methods**

- 1009 The primary focus of this aim is to compare long-term outcomes (cirrhosis) of HCV recurrence in
- 1010 recipients of DDLT vs. LDLT. All participants from the Cohort A2ALL-1 study, including those
- 1011 whose donor was evaluated during the Retrospective era, will be eligible for inclusion. LDLT and
- 1012 DDLT recipients from the new A2ALL sites will be eligible if they had at least one potential donor
- 1013 present to the transplant center for evaluation, as per the original A2ALL-1 inclusion criteria. For
- 1014 these patients identified by the new sites, a waiver of consent for data extraction will be sought from
- 1015 their respective IRBs. for chart review if the patient is deceased or no longer followed. Subjects who
- 1016 received a transplant during the GAP era and meet the inclusion criteria will also be approached for
- 1017 consent or have their data collected under a Waiver of Consent as described above.
- 1018 With the goal of focusing on longer-term outcomes, surviving non-retransplanted recipients (LDLT
- and DDLT) will return to their transplant center at least 3 years post-LT for a comprehensive
- evaluation, including collection of blood for DNA (if not already collected as part of Aim 2) and

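### Aim 2 admits Gap-Period recipients by outcome (failures by waiver, event-free only by consent) but times survival from transplantation, so Gap-stratum survival is biased toward failure

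*Protocol*

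**What the plan says.** Aim 2 compares LDLT with DDLT on patient and graft survival, among other outcomes. Section 3.2.1 fixes the time origin: "Patient and graft survival analysis starting from the time of transplantation".

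Section 4.2.1 sets the entry rule for recipients transplanted in the Gap Period, between the close of A2ALL-1 enrolment and the opening of this protocol. "All A2ALL centers will consent and enroll willing eligible LDLT recipients from the" Gap Period if they have not met an endpoint; "for those who have met study endpoints, data will be collected under waiver" of consent. Section 4.1.1 states the same waiver rule for anyone who enrols after transplant. For A2ALL-1 Cohort recipients of both graft types, Section 4.2.1 says: "Those who have already reached study endpoints (death or graft failure) will have follow-up data" collected by waiver as well.

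The documents differ on who belongs to the Gap stratum of Aim 2:

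- Section 4.2.1 names LDLT recipients only, at every center.
- The Section 3 table of aims by era has no Gap entry for DDLT. It puts Gap LDLT recipients in Aims 1 and 2 at continuing centers, but in Aim 1 only at new centers.
- Appendix D, to which Section 4.2.2 refers for eligibility, lists Gap-era DDLT recipients at continuing centers as eligible for the Core Protocol.

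**The concern.** Whether a Gap recipient is in the data depends on the outcome being analysed. A recipient who has died or lost the graft is counted without being asked. One who is alive with a functioning graft is counted only if found and willing. With the clock started at transplant, the failures are complete and the recipients at risk are a consenting subset. The failure share is too high whenever failures are captured more fully than survivors.

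This matters for Aim 2 because its outcome is survival after LDLT versus DDLT, and two of the three descriptions of the Gap stratum place it on the LDLT side only. A distortion confined to one group passes into the contrast, whereas one shared by both largely cancels.

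**Working it through.** The protocol gives no sample size, power or expected survival for Aim 2, so there is no stated figure to reproduce. The check is selection arithmetic.

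**Inputs**

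- True failure share by enrolment, q: not stated. 10%, 15% and 20% are used as illustrations.
- Share of event-free recipients who consent, c: not stated for Gap recipients. The nearest figure is the Aim 4 assumption in Section 4.4.4, "It also assumes 20% to 30% of prospective recipients will refuse to enroll", so c = 0.7 to 0.8 is borrowed.
- Capture of failures: taken as complete, since they need no consent.
- Gap share of all LDLT recipients, f: not stated. 10% to 40% is assumed.
- True survival for the pooled example: 79%, the 3-year graft survival in Section 2.6 for HCV-infected LDLT recipients after each center's first 20 cases. It is used only as an example.

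**Within the Gap stratum**

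Observed failure share = q / (q + (1 - q)c). The odds of failure are multiplied by 1/c, that is by 1.25 (c = 0.8) to 1.43 (c = 0.7).

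- q = 0.15, c = 0.8: 0.15 / (0.15 + 0.68) = 0.181
- q = 0.15, c = 0.7: 0.15 / (0.15 + 0.595) = 0.201
- q = 0.10: 0.122 to 0.137
- q = 0.20: 0.238 to 0.263

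On the survival scale, a true 79% would read 75.1% (c = 0.8) or 72.5% (c = 0.7).

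**Pooled LDLT arm**

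Take all other LDLT recipients as completely observed, with the same true survival S = 0.79. Observed survival = S(1 - f + fc) / [S(1 - f + fc) + (1 - S)].

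- f = 0.1, c = 0.8: 0.7742 / 0.9842 = 0.787, 0.3 points low
- f = 0.1, c = 0.7: 0.785, 0.5 points low
- f = 0.4, c = 0.8: 0.776, 1.4 points low
- f = 0.4, c = 0.7: 0.6952 / 0.9052 = 0.768, 2.2 points low

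**If the rule acted on both graft types alike**

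Take true survival of 79% and 80%, with everyone in both groups entering under the rule. The groups would read 75.1% and 76.2% at c = 0.8, or 72.5% and 73.7% at c = 0.7. The difference moves only from 1.0 to about 1.1-1.2 points. Distortion of the contrast therefore depends on the Gap stratum being one-sided.

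**The case against.** **No analysis is specified.** Section 4.2 has no statistical subsection, and nothing says Gap recipients will be pooled from transplant without delayed entry. A separate analysis plan could deal with this. That is fair as far as it goes, but the entry rule and the time origin are both fixed in the protocol, and followed as written they produce the bias.

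**Collecting the failures is sensible.** Section 4.5.2.4 calls for including deceased and retransplanted subjects in Aim 5 to avoid survivor bias. This stands. However, Sections 4.5.1 and 4.5.2.4 extend the Aim 5 waiver to recipients lost to follow-up or no longer followed. The Aim 2 waiver covers endpoint cases only.

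**The stratum may not be LDLT-only.** A reader might infer that it is, from Section 4.2.1 and the Section 3 table. Appendix D does not support that. The conflict has to be resolved before one-sidedness can be asserted.

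**The net direction is unknown.** A reader might infer that Aim 2 as a whole is biased against LDLT. The documents do not show this. Setting later LDLT against earlier DDLT would tend to favour LDLT, given the technical progress described in Section 2.5.1, and the two effects may offset each other. The 68% and 79% LDLT graft survival figures in Section 2.6 do not measure an era shift: they are HCV recipients with and without each center's first 20 cases.

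**Some event-free recipients are not wholly absent.** Appendix D says data on former A2ALL subjects are held to 31 August 2010. This softens the loss for them, but not for Gap recipients listed as new subjects, whose existing data source is given as none.

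**Registry data.** The SRTR linkage in Section 4.1.1 updates outcomes in the study population and is not described as covering recipients who never enrolled. The comparison with national data in Section 6.4 could reveal unrepresentative results but would not correct them.

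**Conclusion.** The point holds for the Gap stratum. Outcome-dependent entry combined with a clock started at transplantation overstates failure there whenever failures are captured more fully than survivors. At an assumed 70-80% consent, a true 15% failure share reads as 18-20%.

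The relative inflation of 20-34% that this implies (0.181/0.15 and 0.201/0.15) belongs to the Gap stratum. It should not be read as the error in the Aim 2 contrast. In the pooled LDLT arm the shift is about 0.3 to 2.2 points over the assumed ranges. That is modest, though comparable with the one-point difference (79% versus 80%) in the protocol's own later-case HCV comparison.

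The sizes rest on a refusal rate borrowed from Aim 4, assumed failure and Gap shares, and complete capture of failures. Confounding by era is a separate problem, and no net bias in the LDLT-DDLT contrast is claimed. The disagreement between Section 4.2.1, the Section 3 table and Appendix D over Gap-era DDLT recipients and new centers is an error in its own right.

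**What to change.** 1. In Aim 2 survival analyses, let Gap-era recipients enter the risk set at consent (delayed entry) and leave out pre-consent events known only through the waiver. This removes the bias provided refusal is unrelated to later outcome.
2. Base the primary LDLT-DDLT contrast on A2ALL-1-era recipients at continuing centers, adjusted for transplant year. The restriction to continuing centers is needed because the Section 3 table assigns new-center A2ALL-1-era LDLT recipients to Aim 2 but new-center DDLT recipients to Aim 5 only.
3. In that contrast, censor survivors who do not re-consent at the end of held data, 31 August 2010, and apply the same cut-off to later events known only by waiver. Those who re-consent should rejoin the risk set at re-consent; crediting them with the interval in between would create the opposite bias.
4. Report Gap and A2ALL-2 LDLT recipients descriptively.
5. Reconcile Section 4.2.1, the Section 3 table and Appendix D on whether Gap-era DDLT recipients and new-center Gap recipients belong to Aim 2.

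Items 1 to 4 need analysis-plan wording and item 5 a protocol clarification. The price is fewer LDLT recipients and fewer early Gap-era events in the comparison. Obtaining status on every Gap-era transplant from SRTR would avoid that loss, but it means using data on people who have not consented. That would need wider approval under the IRB oversight and data use agreement described in Section 5.1.
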